DURATION OF INVESTIGATIONAL AGENT ADMINISTRATION AND STUDY PARTICIPATION

Duration of UC-961 administration is until disease progression, treatment intolerance, or lack of clinical benefit. Patients may remain on the clinical trial protocol until one of the following:

- Clinical or radiographic progressive disease (See Section 12).
- Adverse Events requiring removal from study (See Section 13).
- Refusal of further protocol therapy by patient/parent/guardian
- Non-compliance that in the opinion of the investigator does not allow for ongoing participation.
- Physician determines it is in the patient's best interest to discontinue participation in the clinical trial.
- Completion of all clinical trial procedures.

	Participation in the study and long-term follow-up will continue until one of the following:
	Death.
	Loss to follow-up.
	Withdrawal of consent for any further data submission.
	Progression requiring initiation of subsequent therapy.
	UC-961 is administered by intravenous infusion on day 1, 15, 29, 43, 57, 85, 113, and 141, after which responses will be assessed.
STUDY DRUG ADMINISTRATION	Patients with an objective response (meeting working group criteria for partial response or complete response) will continue at the same dose and schema. Patients with stable disease or progressive disease are eligible to increase the dose of UC-961 for another 6-month course.
CRITERIA TO EVALUATE SAFETY	Safety will be determined by Principal Investigator, and will be assessed according to the NCI Common Terminology Criteria for Adverse Events version 4.03 (NCI CTCAE v4.03) for non-hematologic toxicity and modified iwCLL criteria for hematologic toxicity.
CRITERIA TO EVALUATE EFFICACY	Overall response rate is the percentage of patients meeting criteria for partial response, nodular partial response, or complete response based on iwCLL criteria. Progression free survival is according to iwCLL definition.

Completed UC-961 Phase 1 Clinical Trial (UC-961 q 14 days x 4 doses)

Screen for eligibility for UC-961 Extension Trial

- √ Tolerated UC-961 without dose limiting toxicity and recovered from toxic effects to grade 1 or baseline.
- √ If intervening CLL therapy, maintains measurable disease.

UC-961 q 14 days x 4 doses, then q 28 days x 4 doses (dose based on ongoing phase 1 trial)

Response assessment (labs, imaging, bone marrow biopsy)

Repeat UC-961 course (dose increase if PD or SD)

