1.4 Rationale for Dose Selection

Each extension course consists of 8 infusions. A patient may repeat the course, and therefore receive a total of 16 infusions on the extension study. Each individual patient will receive the same

dosage of UC-961 for each of the 8 infusions of each course. The dosage of UC-961 may be increased for the 2nd set of 8 infusions (if a higher dose has been shown to be safe on the phase 1 trial AND there is Progressive Disease or Stable Disease after the first course of extension.

The dose administered on this extension study will be the highest safe dose, or once established, the biologically active dose or the recommended phase 2 dose from the phase 1 trial. To date, the 8 mg/kg dose level has been completed and determined to be safe. Therefore, patients on this extension study will begin at the 8 mg/kg dose level. Should subsequent dose levels be determined to be safe in the Phase 1 trial, the dose utilized in this trial may increase for subsequent patients.

Planned dose levels (starting dose is the highest safe dose administered to a patient in the phase 1 trial):

Potential	Dose		
Dose Level			
-1	4 mg/kg		
1 (start)	8 mg/kg		
2	16 mg/kg (or max 2000 mg dose)		
3	20 mg/kg (or max 2000 mg dose)		

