4.0 INVESTIGATIONAL TREATMENT PLAN

4.1 Dose Assignment

The dose of UC-961 is currently undergoing evaluation in a phase 1 study.

During the extension treatments, patients will be assigned to receive the highest safe dose from an ongoing phase 1 study, or the established maximum tolerated dose/ recommended phase 2 dose (which may increase as the phase 1 trial accrues additional patients). Patients will receive the same dose of UC-961 for 1 course, which consists of 8 doses (every 14 days for 4 doses, then every 28 days for 4 doses). As of April 2016, the highest safe dose is 8 mg/kg.

Following 1 course, patients will be assessed for response, and then are eligible to receive a second course. Patients with a complete response or partial response will continue at the same

dose. Patients with stable disease or progressive disease will receive a higher dose of UC-961, if a higher safe dose has been established in the concurrent CLL Phase 1 trial by that time.

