4.8 Prohibited concomitant therapy

Concurrent Anticancer Therapy

Concurrent cancer therapy, including chemotherapy, radiation therapy, immunotherapy, or biologic therapy may NOT be administered to patients receiving study drug. Corticosteroids administration, even if for treatment of conditions other than CLL, at doses greater than

prednisone 20 mg daily (or equivalent dose of other steroids) are prohibited for greater than 14 days. If these treatments are administered the patient will be removed from study.

Investigational Agents

No other investigational agents may be given while the patient is on study.

4.9 **Duration of Therapy**

The investigational agent UC-961 will be administered until:

- a) Clinical or radiographic progressive disease.
- b) Unacceptable toxicities.
- c) Refusal of further protocol therapy by patient.
- d) Non-compliance that in the opinion of the investigator does not allow for ongoing participation.
- e) Completion of therapy.
- f) Physician determines it is in the patient's best interest to discontinue study agent.

Clinical Study Stopping Rules: Enrollment will be held pending review and approval by the UC San Diego Moores Cancer Center Data Safety Monitoring Board (DSMB) in the event of either of the following:

- Death. or
- 2 or more non-hematologic Grade 4 events at least possibly attributable to the study drug.

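### Course-2 dosing rules conflict: escalation is not barred after every toxicity reduction, progressive disease is both a stop and a retreatment trigger, and two dose windows are printed

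*Combined protocol and SAP*

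**What the plan says.** **Stopping.** The synopsis states: "Duration of UC-961 administration is until disease progression, treatment intolerance, or lack of clinical benefit". Section 4.9(a) lists "Clinical or radiographic progressive disease" among the events that end UC-961. Neither makes an exception or refers to Section 4.1. Section 4.9(f) separately lets the physician judge it in the patient's "best interest to discontinue study agent".

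**Retreating.** Section 4.1: "Patients with stable disease or progressive disease will receive a higher dose of UC-961, if a higher safe dose has been established" in the concurrent phase 1 trial by then. Section 1.4: "The dosage of UC-961 may be increased for the 2nd set of 8 infusions" if a higher dose has proved safe in phase 1 "AND there is Progressive Disease or Stable Disease after the first course of extension". Synopsis dosing row: "Patients with stable disease or progressive disease are eligible to increase the dose of UC-961 for another 6-month course". Synopsis schema: "Repeat UC-961 course (dose increase if PD or SD".

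**Timing.** Section 5.4 lists course-2 doses on Days 197, 211, 225, 239, 253, 281, 309 and 337 with ±7 days. Section 6.0 lists the same days with ±3. Footnote 7 to Section 6.0 alternatively dates course 2 at 28 days after Response Assessment 1. Footnote 6 lets that assessment be brought forward when PD is suspected.

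**Reductions.** Section 4.6.1 requires the next lower dose level after a first Grade 2 or higher confusion/delirium, pneumonitis or acute kidney injury, and after a second qualifying hematologic event. Its note 3 says re-escalation is not planned when the reduction was for Grade 3 or 4 toxicity.

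**The concern.** These rules settle who is dosed in course 2, when, and at what level, in a trial whose primary objective is safety with extended dosing. As written they cannot all be followed.

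- The main safety question is whether a patient whose dose was lowered for toxicity can be escalated because the disease is stable or progressing.
- For a patient with PD at the end of course 1, Section 4.9 read alone stops drug and Section 4.1 read alone offers another course.
- For every course-2 patient, two dose windows are in force.

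**Working it through.** The plan has no sample size, power or error rate on this point. The check is a comparison of texts plus arithmetic on the printed days and doses.

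**1. Escalation after a reduction.** The inputs are the dose levels in Section 1.4 (4, 8, 16 and 20 mg/kg, the last two capped at 2000 mg) and the reduction rules in 4.6.1. Each kind of reduction is set against note 3:

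- Grade 3 or 4 non-hematologic event: covered by note 3.
- Hematologic event graded 4 on the Section 7.1.2 scale: covered.
- First Grade 2 confusion, pneumonitis or acute kidney injury: reduction required, not covered.
- Hematologic event in a patient whose baseline is too low to grade: possibly not covered. Section 7.1.2 treats neutrophil toxicity as not evaluable when baseline ANC is below 1,500/μL, and hemoglobin toxicity as not evaluable when baseline is below 10 g/dL. The asterisk under 4.6.1 still applies holds and adjustments when baseline values are below its thresholds. Such a reduction may carry no grade.

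For a patient reduced from 8 to 4 mg/kg, the possible steps are 8/4 = 2 times, 16/4 = 4 times and 20/4 = 5 times, depending on the level phase 1 has cleared. The cap lowers the last two multiples above 2000/16 = 125 kg and 2000/20 = 100 kg. The 8 mg/kg level is already described as safe, so the twofold step needs no further phase 1 result.

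A Grade 2 trigger is not hypothetical. The phase 1 adverse event summary before Section 1.4 shows one Grade 2 confusion, judged unlikely to be related. Section 4.6 exempts only events definitely unrelated to the drug, so a similar event here would call for a reduction.

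**2. PD at the end of course 1.** Two places stop drug (4.9(a), synopsis duration text). Four allow a second course (4.1, 1.4, synopsis dosing row, schema). The difference is 0 or 8 further infusions over 337 − 197 = 140 days. For a patient who completed course 1, 8 + 8 = 16, which matches the total in Section 1.4.

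**3. Windows.** Response Assessment 1 falls on Day 169 ± 7, that is 162 to 176. Adding 28 gives Day 190 to 204, which equals 197 ± 7. Carrying 14- and 28-day spacing forward reproduces all eight days in Section 5.4 with ±7, ending at 330 to 344 (337 ± 7). So ±7 is coherent as a shift of the whole calendar. No text says this, or says whether the ±3 in Section 6.0 runs from the printed days or from the footnote 7 date:

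| Reading | First course-2 dose |
|---|---|
| 5.4, ±7 on Day 197 | Day 190–204 |
| 6.0, ±3 on Day 197 | Day 194–200 |
| ±3 added to the footnote 7 date | Day 187–207 |

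The first and third ranges match footnote 7 only if the assessment is on Day 169 ± 7. If footnote 6 is used, course 2 can start earlier.

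If the window applies separately to each dose, the permitted gap is g ± 2w, for planned gap g and window w:

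| Planned gap | w = 3 | w = 7 |
|---|---|---|
| 14 days | 8–20 | 0–28 |
| 28 days | 22–34 | 14–42 |

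**The case against.** **On PD.** The four retreatment passages are specific to the end-of-course assessment, and 4.9(a) is a general list. Reading the specific over the general leaves only a missing cross-reference. This largely stands: the intent is evident. A reader might infer that the plan gives no dose for a PD patient when nothing higher has been cleared. The documents do not support that. Section 4.1 assigns the highest safe dose, and Section 1.4 makes the increase conditional, so the same dose is implied. What remains unstated is whether such a patient should be retreated at all.

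**On windows.** A reader might infer that ±7 allows two doses on the same day. That is the literal limit of a per-dose reading. Section 5.4 itself asks for 14-day spacing, and the calendar-shift reading with ±3 per dose keeps gaps at 8–20 and 22–34 days. The point is minor.

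**On escalation.** Only Section 4.1 is mandatory; 1.4 and the synopsis are permissive. Note 3 names Grades 3 and 4 expressly, so allowing re-escalation after a resolved Grade 2 event may be deliberate. A repeat of confusion, pneumonitis or kidney injury already means discontinuation, the physician can stop drug under 4.9(f), and only doses found safe in phase 1 can be used. These limits are real. They still leave a mandatory sentence to be overridden by individual judgement. If re-escalation is intended, the protocol should say so.

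**Conclusion.** The rules conflict as written and should be aligned.

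- **Escalation after a toxicity reduction** is the main point. It concerns patients with stable or progressive disease reduced for a first Grade 2 confusion, pneumonitis or kidney injury, and possibly those with ungraded hematologic reductions. The possible step is 2, 4 or 5 times the reduced dose (less where the cap binds), assuming a reduction from 8 to 4 mg/kg and phase 1 clearance of the higher level.
- **The PD rule** is a missing exception. It decides between 0 and 8 further infusions; the total of 16 assumes course 1 was completed.
- **The windows** are a minor inconsistency.

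The documents do not say how many patients fall in any group, so no frequency can be given. A reader might infer that the safety analysis is compromised. It is not: under Section 10.0 one dose makes a patient evaluable, so the safety set is the same under either reading.

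**What to change.** 1. **Escalation.** Add to the escalation sentence in Section 4.1: *except patients whose dose was reduced for toxicity under 4.6.1*. Extend note 3 to all toxicity reductions, including Grade 2 and ungraded hematologic ones.
2. **PD.** Amend Section 4.9(a) and the synopsis duration text to: *Progressive disease, except PD at Response Assessment 1 after completing course 1, where Section 4.1 applies*. The sponsor should confirm two decisions: whether PD patients are retreated when no higher safe dose exists, and whether drug stops when PD is found at an early assessment under footnote 6. The proposed wording stops the latter group.
3. **Windows.** Set Section 5.4 to ±3 days per dose, with doses 2 to 8 timed from the actual course-2 Day 1, which footnote 7 sets.

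The cost is protocol wording and two clinical decisions, with no added procedures or patients. The downside is that a few patients with resolved Grade 2 events would stay at the lower dose. No change to the response or progression-free survival definitions is needed.

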4.2 Dose Limiting Toxicity

Dose-Limiting Toxicity (DLT) is defined as any of the following adverse events that are considered by the investigator to be possibly, probably, or definitely related to the study agent UC-961 within the 28 days of the start investigational treatment:

- CTCAE Grade 3 or higher non-hematologic toxicity, except for: Grade 3 infections lasting < 7 days that have resolved, or one occurrence of Grade 3 infusion reaction; or
- Grade 4 or higher hematologic toxicity (by modified iwCLL criteria); or
- Any AE requiring a dose delay of greater than 28 days;

4.3 Recommended Pre-Medications and Concomitant Medications

- 1. Antibiotics: per investigator discretion.
- 2. Tumor lysis syndrome prophylaxis: allopurinol or other uric acid lower agent per investigator discretion.
- 3. Infusion reaction prophylaxis:
 - Acetaminophen 325-1000 mg PO prior to UC-961 administration, or per investigator discretion.
 - Benadryl 50 mg IV or PO, or other antihistamine per investigator discretion, prior to UC-961 administration.
 - Optional: Hydrocortisone 100 mg IV bolus (or infusion over 30 +/-10 minutes) or other equivalent corticosteroid, prior to UC-961 infusion.

4.4 UC-961 infusion plan

Initial Infusion (Cycle 1, Day 1, or if longer than 56 day since prior UC-961 infusion)

- 1. **Test Dose:** Infuse 8 mg/hour for 10 minutes, then stop infusion (or sooner if not tolerated prior to 10 minutes). 10 minutes (+/-5 minutes) following completion of test dose, monitor for any signs or symptoms of infusion reaction, including: hypotension (greater than 30 mm Hg drop in systolic blood pressure from baseline); fever (temperature greater than 101.3 degrees Fahrenheit); rigors. Management / supportive measures for these events is per institutional standards.
- 2. In the absence of any of vital sign instability or signs/symptoms of infusion reaction, or after normalization of them, begin infusion:
 - Initiate infusion at 25 mg/hr x 30 min (+/- 5 minutes)
 - Check vital signs every 30 minutes (+/- 5 minutes).
 - If vitals signs are stable (SBP is within 20 mm Hg of baseline, HR > 60 or < 120 beats per minute or within 20% of baseline, and temperature <101.3 F) and without sign/symptoms of infusional toxicity, the rate of infusion is doubled every 30 minutes (+/- 5 minutes) to a maximum of 800 mg/hr for remainder of infusion.

- If a patient is unable to tolerate faster rate, continue infusion at the best tolerated rate until infusion is completed. Monitor for acute infusion-related reactions during and for 30 minutes (+/- 5 minutes) after infusion completed.
- Hold infusion and immediately notify MD if any of the following occur: hypotension (greater than 30 mm Hg drop in systolic blood pressure from baseline); fever (temperature greater than 101.3 degrees Fahrenheit); rigors. Management / supportive measures for these events is per institutional standards. Infusion of UC-961 is resumed at half the previous rate once vital signs and symptoms have returned to baseline.

Subsequent Infusions

- 1. Test dose is not required.
- 2. Initiate infusion at rate of 50 mg/hr (or at highest previously tolerated rate if it is lower than 50 mg/hr). Remainder of infusion, vital sign monitoring, and management of infusion reaction as above.

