4.6.2 Modifications for Infusion Reactions

Patients will be monitored for the presence of infusion-related reactions. Treatment for infusion-related reactions will be managed according to the following guidelines:

Infusion Reaction	Occurrence	Management Guidelines
Grade ≤ 2	any	Institute supportive measures.
		When resolved, resume study treatment at same dose level. Infusion rate adjustment per 4.4.
Grade 3	1st	Institute supportive measures.
		When resolved, resume study treatment at the same dose level. Infusion rate adjustment per 4.4. Premedications listed in protocol are mandatory for rechallenge.
	2nd	Institute supportive measures.
		Permanently discontinue study treatment.
Grade 4	any	Institute institutional procedures for adult medication reaction/anaphylactic response.
		Permanently discontinue study treatment.

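### The heart-rate condition for doubling the infusion rate is met by every heart rate as written; the first 'or' in Section 4.4 should be 'and'

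*Combined protocol and SAP*

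**What the plan says.** Section 4.4 sets the conditions for raising the infusion rate. Three vital signs and one clinical condition must all be satisfied:

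- Blood pressure: "If vitals signs are stable (SBP is within 20 mm Hg of baseline".
- Heart rate: "HR > 60 or < 120 beats per minute or within 20% of baseline".
- Temperature and symptoms: "and temperature <101.3 F) and without sign/symptoms of infusional toxicity".

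If they are met, "the rate of infusion is doubled every 30 minutes (+/- 5 minutes) to a maximum of 800 mg/hr for remainder of infusion".

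The same section has a separate stopping instruction: "Hold infusion and immediately notify MD if any of the following occur: hypotension (greater than 30 mm Hg drop in systolic blood pressure from baseline"), with fever and rigors as the other two triggers. It gives no heart-rate value.

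Two other places rely on the same rule. For infusions after the first, Section 4.4 says "Remainder of infusion, vital sign monitoring, and management of infusion reaction as above". For a first Grade 3 infusion reaction, Section 4.6.2 says "When resolved, resume study treatment at the same dose level. Infusion rate adjustment per 4.4"; the row for Grade 2 or lower also refers back to 4.4.

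**The concern.** The heart-rate clause joins a lower limit and an upper limit with 'or'. Two one-sided limits that overlap, joined this way, cover the whole number line, so the clause imposes no limit. The final alternative, closeness to baseline, is an allowance for patients who fall outside a normal range. It has a purpose only if the first part defines such a range, which points to a drafting slip for 60 to 120.

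What is at stake is infusion safety. The primary objective (Section 2.1.1) is safety and tolerability, and Section 9.1 names infusion reaction as a possible class effect. Under the literal text, doubling the rate in a patient with a heart rate of 150 complies with the protocol as long as the other conditions are met, and would not be recorded as a deviation.

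No sample size, estimate or endpoint definition depends on this clause. Section 4.2 also exempts one Grade 3 infusion reaction from the definition of dose-limiting toxicity.

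**Working it through.** The plan states no figure to reproduce. The check is one of logic, with counts to show its reach.

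**Inputs.** The limits of 60 bpm, 120 bpm and 20% of baseline, the starting rates of 25 and 50 mg/hr, the 800 mg/hr maximum, the 30-minute steps and the test dose are from Section 4.4. The 8 infusions per course and the 8 mg/kg dose are from Sections 1.4 and 4.1. The baseline heart rates are assumed for illustration.

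**Rule as written.** Pass if HR > 60, or HR < 120, or |HR − baseline| ≤ 0.20 × baseline.

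- Any HR of 60 or less is below 120, so it passes.
- Any HR of 120 or more is above 60, so it passes.
- Anything in between meets both limits.

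The clause therefore blocks 0 of the 201 whole-number rates from 20 to 220 bpm, whatever the baseline. Widening the range to 0 to 300 gives 0 of 301. Both 35 and 170 bpm meet it. Commas separate the clause from the blood-pressure and temperature conditions, and regrouping the 'or' terms makes no difference.

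**Rule with 'and'.** Pass if (HR > 60 and HR < 120), or |HR − baseline| ≤ 0.20 × baseline.

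| Baseline (assumed) | Within 20% | Passing range | HR 40 | HR 130 | HR 150 |
|---|---|---|---|---|---|
| 50 | 40–60 | 40–119 | passes | fails | fails |
| 60 | 48–72 | 48–119 | fails | fails | fails |
| 70 | 56–84 | 56–119 | fails | fails | fails |
| 80 | 64–96 | 61–119 | fails | fails | fails |
| 100 | 80–120 | 61–120 | fails | fails | fails |
| 110 | 88–132 | 61–132 | fails | passes | fails |

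As written, every cell in the last three columns would be a pass.

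**How often the rule is used.**

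- First infusion: 25 → 50 → 100 → 200 → 400 → 800 mg/hr, 5 doublings.
- Each later infusion: 50 → 100 → 200 → 400 → 800 mg/hr, 4 doublings.
- One course of 8 infusions: 5 + 7 × 4 = 33 doublings at most.

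**Whether the top step is reached in practice.** Drug given before 800 mg/hr, at 0.5 hours per step:

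- First infusion: (25 + 50 + 100 + 200 + 400) × 0.5 = 387.5 mg. The test dose adds 8 mg/hr × 10/60 hr = 1.3 mg, for 388.8 mg in all.
- Later infusions: (50 + 100 + 200 + 400) × 0.5 = 375 mg.

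At 8 mg/kg, patients above 388.8/8 = 48.6 kg (first infusion) or 375/8 = 46.9 kg (later infusions) reach every step, assuming no holds or rate reductions.

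**Whether another section supplies the limit.** The hold triggers in 4.4 have no heart-rate value, and 4.6.2 adds none. Sections 5.2.8 and 5.4.8 measure pulse after the infusion, when the rate decisions have already been made, and attach no threshold. ECG is required only at screening (5.1.3).

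**The case against.** The strongest reply is that this is a slip whose meaning is obvious. Staff would probably read it as 60 to 120, and a nurse seeing 150 bpm against a baseline of 70 is unlikely to call that stable. Marked tachycardia could also be judged a sign of infusional toxicity, which blocks doubling on its own. Section 4.4 has further safeguards: the main infusion starts only once there is no vital-sign instability, it resumes after a hold only when vital signs are back to baseline, and a patient who cannot tolerate a faster rate stays at the best tolerated one. Enrolled patients have also completed earlier UC-961 infusions without dose-limiting toxicity, and the phase 1 adverse event table shows only Grade 1 and 2 events.

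Much of this stands as a limit on the practical impact. It does not remove the error. Those safeguards depend on judgement or apply at other steps, and none gives a heart-rate number for doubling the rate. The phase 1 experience is only partial reassurance, since some patients may now receive a higher dose than before.

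Two more points stand. The count of 33 is a maximum number of rate decisions; it does not say how often heart rate would be the only abnormal sign, and the documents give no basis for estimating that. And the corrected rule still admits large rises: at a baseline of 50, a rate of 119 passes, which is (119 − 50)/50 = 138% above baseline. The correction restores the absolute ceiling that the text appears to intend, and no more.

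**Conclusion.** The concern holds. The heart-rate clause in Section 4.4 is wrong as written: it excludes no heart rate at any baseline, and it governs up to 33 rate decisions per course. That conclusion is pure logic and needs no assumption. The corrected passing ranges rest on assumed baselines and on the inferred intent of a 60 to 120 range with an allowance around baseline.

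This is a wording error in an operational safety rule. It should be corrected. The remaining conditions for doubling keep it from being more serious, and no endpoint, dose-limiting toxicity definition or statistical calculation is affected.

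**What to change.** In Section 4.4, change the first 'or' to 'and' and add brackets, so that the condition is: (HR > 60 and < 120 bpm) or within 20% of baseline.

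The brackets matter. If the text were instead taken as HR > 60 and (HR < 120 or within 20% of baseline), a patient with a baseline of 50 would fail at their own resting rate. The clinical team should confirm that the first grouping is the intended one.

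The cost is one word and a pair of brackets. The later-infusion text in 4.4 and the reaction table in 4.6.2 refer back to this rule and need no change.

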4.6 Dose Modifications and Dosing Delays

Each patient will be assessed for the development of toxicity according to the NCI Common Toxicity Criteria for Adverse Events (CTCAE), version 4.03 for non-hematologic toxicity or modified iwCLL criteria (section 7.1.2) for hematologic toxicity. Patients experiencing a DLT as defined in section 4.2 will be discontinued from study treatment. Otherwise, dose adjustments should be made according to the system showing the greatest degree of toxicity, as per 4.6.1, unless the adverse event is definitely unrelated to the study drug. Dose levels are listed in section 1.4.

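### The restart instructions in section 4.4 carry no grade or occurrence limit, so for a Grade 4 or second Grade 3 infusion reaction that meets their triggers they contradict the permanent stop in section 4.6.2

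*Combined protocol and SAP*

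**What the plan says.** **Section 4.4, after the test dose.** "In the absence of any of vital sign instability or signs/symptoms of infusion reaction, or after normalization of them, begin infusion". The test dose applies to the initial infusion, or when more than 56 days have passed since the previous one.

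**Section 4.4, during the infusion.** "Hold infusion and immediately notify MD if any of the following occur": a systolic drop of more than 30 mm Hg, a temperature above 101.3 F, or rigors. The restart sentence follows: "Infusion of UC-961 is resumed at half the previous rate once vital signs and symptoms have returned to baseline". For later infusions the test dose is not required, but the rest carries over: "Remainder of infusion, vital sign monitoring, and management of infusion reaction as above".

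**Section 4.6.2.** The table has four rows. Grade 2 or lower, and a first Grade 3, lead to resumption at the same dose level. The first Grade 3 row adds: "Infusion rate adjustment per 4.4. Premedications listed in protocol are mandatory for rechallenge". The second Grade 3 row and the Grade 4 row both end with: "Permanently discontinue study treatment".

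**Sections 4.2 and 4.6.** "Patients experiencing a DLT as defined in section 4.2 will be discontinued from study treatment". The definition in 4.2 exempts only a single Grade 3 infusion reaction. It requires at least a possible relation to UC-961 and onset within 28 days of treatment start.

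**The concern.** Section 4.4 makes restart depend only on recovery. Section 4.6.2 makes it depend on grade and occurrence. For the most severe reactions the first permits more drug and the second rules it out. The link between them runs one way: two rows of 4.6.2 point to 4.4, and 4.4 never points to 4.6.2.

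Two things are at stake. The first is safety: a patient could be re-infused after an event for which the protocol's own table ends treatment. The second is interpretation of the safety data, which are the primary aim of the study. Whichever section staff follow in such a case, they depart from the other, so the plan gives no basis for deciding whether a restart was a protocol deviation. If dosing then continued, the exposure recorded after the reaction, and possibly the proportion withdrawn for adverse events that section 10.0 plans to report, would reflect which section was read.

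**Working it through.** The plan gives no figure to reproduce on this point. The check is a comparison of the texts, with simple counting to show how far each rule reaches.

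**Step 1. Instruction by grade and occurrence, for a reaction that meets a 4.4 trigger and then settles.**

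| Infusion reaction | 4.4 | 4.6.2 | Result |
|---|---|---|---|
| Grade 2 or lower, any | restart | resume, rate per 4.4 | agree |
| Grade 3, first | restart | resume, rate per 4.4, premedication mandatory | agree on restart; 4.4 omits the premedication condition |
| Grade 3, second | restart | permanent stop | conflict |
| Grade 4, any | restart | permanent stop | conflict |

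Two of four rows conflict.

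**Step 2. Can a severe reaction meet the 4.4 triggers?** Yes. The triggers are defined by signs, not by CTCAE grade. The hypotension trigger has a lower bound and no upper bound, so a severe fall in pressure meets it as well as a moderate one. The test-dose sentence is wider: it covers any vital sign instability or sign or symptom of infusion reaction.

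**Step 3. Which infusions does each restart sentence cover?** Section 1.4 allows up to 16 infusions per patient (two courses of 8).
- The resume sentence covers all 16, because 4.4 carries reaction management over to later infusions.
- The test-dose sentence covers the first infusion and any infusion after a gap of more than 56 days. On nominal days the gap between courses is 197 − 141 = 56 days, which is not more than 56. On nominal timing, then, it applies once; visit windows or delays could bring it in again.

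**Step 4. How much does the DLT route add?** A Grade 4 reaction, or a second Grade 3, is a DLT under 4.2 if it is at least possibly related and inside the window, and 4.6 then discontinues the patient. The first infusions fall 0, 14, 28 and 42 days after Day 1. Assuming that the window starts at Course 1 Day 1 and is not reopened for Course 2, it holds two infusions, or three if the 28th day is counted. That leaves 16 − 3 = 13 or 16 − 2 = 14 infusions to which only 4.6.2 applies. The stop in 4.6.2 has no time or attribution limit, so it carries the point without the DLT route.

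**Step 5. Does another section settle it?** Steps 5.2.7 and 5.4.7 refer to 4.3, 4.4 and 4.5 (5.2.7 also to 4.1), and neither names 4.6.2. Section 4.5 withholds a dose only for toxicity that is still ongoing, so a reaction that has resolved does not fail it. Section 4.6 sends dose adjustments to 4.6.1. No sentence ranks 4.6.2 above 4.4.

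**The case against.** The best reply is that the two sections do different jobs. Section 4.6.2 opens by saying that infusion reactions will be managed by its table. It refers to 4.4 only for Grade 2 or lower and a first Grade 3, and only for the rate. On that reading 4.6.2 decides whether to restart and 4.4 decides how fast; 4.4 is merely silent on grade, and what is missing is a cross-reference. The hold instruction also requires a physician to be told at once, so restart is not left to infusion staff.

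Much of this stands. The combined reading is plausible, and a careful reader may well adopt it. But no sentence states it, and 4.4 gives its own condition for restart, return to baseline, without asking anyone to grade the reaction or check 4.6.2. Notifying a physician does not tell the physician which section applies.

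Three stronger readings are tempting, and the documents do not support them:
- *That the resume sentence covers any infusion reaction.* It follows three named signs. A reaction during the main infusion with none of them is outside it.
- *That the number of DLTs, or of discontinuations for DLT, depends on which section is followed.* DLT status turns on grade, attribution and timing. Restarting the infusion does not change it, and a same-day restart does not cancel the discontinuation required by 4.6.
- *That staff work from 4.4 alone at the bedside.* The documents do not say so. They show only that the infusion-day steps cite 4.4 and not 4.6.2.

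**Conclusion.** The point holds as a conflict between stated rules. For a Grade 4 or second Grade 3 reaction that meets a 4.4 trigger, 4.4 read literally allows restart and 4.6.2 ends treatment permanently. This covers two of the four rows of the 4.6.2 table and, through the resume sentence, every infusion. It rests on reading each section as written, since the plan states no order of precedence.

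Its frequency cannot be derived. A reader might multiply the ceiling of 33 × 16 = 528 infusions by a guessed rate, but the text available gives no rate of severe infusion reactions. The phase 1 adverse-event summary in the background lists only Grade 1 and 2 events and has no row for infusion reactions, and entrants must have tolerated UC-961 without a DLT. Such events may therefore be rare. The case for correction rests on the consequence of a single event, not on a count. Nothing here says which of the two rules is clinically right.

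**What to change.** The sponsor must reconcile 4.4 with 4.6.2 and 4.6, and state which section governs restart for each grade and occurrence of infusion reaction. That statement should be cross-referenced at both restart sentences in 4.4: the one after the test dose and the one after a hold. The same edit can settle whether the premedication condition for a first Grade 3 rechallenge applies when 4.4 is followed. Adding the governing section to steps 5.2.7 and 5.4.7 would complete the link.

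The cost is a few lines of protocol text, with whatever IRB review an amendment needs. Sample size, visit schedule, data collection and analysis are unchanged.
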